A double-blind, placebo-controlled, randomized study examining the effects of nebivolol compared to atenolol on endothelial function and cardiovascular risk in patients with early vascular disease.

EVIDENCE: Early Vascular Impairment-Determine Efficacy of Nebivolol, Comparator Examination

Principal Investigator: [name]

Co-Investigators: [name], PhD
[name]
[name]

Version Date: January 14, 2014

University of Minnesota Medical School, Cardiology Division

PI Contact Information:

Mail: [name]
[name]

[contact]

[contact]

e-mail: [contact]

Table of Contents

STUDY SCHEMA	3
1. INTRODUCTION AND SCIENTIFIC RATIONALE	4
2. STUDY DESIGN	4
3. METHODOLOGY	4
4. OBJECTIVES	5
5. SELECTION OF PATIENTS	6
6. RANDOMIZATION PROCEDURES	7
7. TREATMENT PLAN	8
8. STUDY PARAMETERS	10
9. STUDY ENDPOINTS	12
10. ADVERSE EVENT REPORTING	13
11. DATA AND SAFETY MONITORING PLAN	16
12. STATISTICAL CONSIDERATIONS	16
13. ADMINISTRATIVE REQUIREMENTS	17
14. REFERENCES	18

STUDY SCHEMA

[figure not shown]
Study Population:

- Males and females between 18 and 80 years of age with early vascular disease
- Borderline blood pressure (120-145/80-90 mm Hg)
- Borderline or abnormal small artery elasticity (C_2) as measured by pulse contour analysis
- Treatment-naïve for all blood pressure medications including diuretics for at least 30 days prior to baseline visit
- No known history of cardiovascular disease

Accrual Goals:

75 patients enrolled.

Treatment Plan:

Schedule of Assessments:

- **Blood pressure at rest at 0, 1, 3, 6 and 9 months**
- **Small artery elasticity (C_2) and flow-mediated dilation at 0, 1, 3 and 9 months**
- **Rasmussen Disease Score assessments** (large artery elasticity, carotid intima-medial thickness, electrocardiogram (ECG), treadmill exercise test and left ventricle ultrasound) **at 0, 3 and 9 months**
- **Cardiac Health Biomarkers** (Total cholesterol, LDL, HDL, triglycerides, glucose, hsCRP, microalbuminuria and NT-proBNP) **at 0, 3 and 9 months**

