1. INTRODUCTION AND SCIENTIFIC RATIONALE

β -blockers have been widely used for the treatment and prevention of cardiovascular disease for more than three decades. In recent years, β -blocker usage has declined as studies have shown that traditional β -blockers have little effect on peripheral resistance, which is increased in individuals with endothelial (vascular) dysfunction [1-3]. Recently, nebivolol, a third generation β -blocker, was approved for use in the United States.

Nebivolol is a highly selective β_1 -blocker with vasodilating effects that reduce peripheral resistance. Vasodilation is mediated by nebivolol's action at multiple points in the nitric oxide (NO) pathway [4]. The NO-mediated vasodilation of nebivolol is novel among β -blockers and is particularly promising as impaired vascular function in patients with cardiovascular disease may be due in part to decreased endothelial NO bioavailability [5]. Studies in patients with hypertension and/or coronary artery disease have shown that nebivolol improves endothelial function while non-vasodilating β -blockers do not [6, 7]. The efficacy of nebivolol on endothelial function in low to moderate risk populations has not been well documented.

We propose to study nebivolol in subjects with early vascular disease, using atenolol as an active comparator, as both drugs are selective β_1 -blockers with no α -blocking capabilities. These drugs differ in the fact that atenolol does not have vasodilating properties [6]. We hypothesize that both drugs will likely lower blood pressure through β_1 -receptor blocking but only nebivolol will improve impaired endothelial function, presumably through NO-mediated vasodilation. A placebo arm will also be employed to further differentiate these two treatment strategies.

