5.1 Inclusion criteria

- Males and females 18-80 years of age
- Borderline blood pressure (120-145/80-90 mm Hg)
- Borderline or abnormal small artery elasticity (C₂) as measured by pulse contour analysis
- Treatment-naïve for all blood pressure medications including diuretics for at least 30 days prior to baseline visit
- Able to walk on a treadmill for 3 minutes
- Female patients with reproductive potential must use an approved contraceptive method if appropriate (for example, intrauterine device [IUD], birth control pills, or barrier device) during and for 1 month after the last dose of study drug.
- Voluntary written informed consent before performance of any study-related procedure not part of normal medical care, with the understanding that consent may be withdrawn by the subject at any time without prejudice to future medical care.

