6. RANDOMIZATION PROCEDURES

Randomization will occur after informed consent has been obtained and after eligibility is confirmed by measuring blood pressure and small artery elasticity. Two 1:1:1 randomization lists (one for subjects taking a statin and one for subjects without statin therapy) generated by variable block randomization will be used to assign each subject to a study arm at the time of enrollment. This method will allow stratification of statin therapy.

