8. STUDY PARAMETERS

8.1 Schedule of Events

Procedure/measurement	Screen	Baseline	1 Month	3 Months	6 Months	9 Months
Resting blood pressure	x		x	x	x	x
Arterial elasticity (small and large)	x		x	x		x
Treadmill exercise test		x		x		x
Carotid intima-medial thickness		x		x		x
Electrocardiogram		x		x		x
Left ventricle ultrasound		x		x		x
Retinal photo		x		x		x
Flow-mediated dilation		x	x	x		x
Blood draw		x		x		x
Urine sample collection		x		x		x
Physical examination		x		x		x
Medical history		x				

Blood and urine analysis	Code	Baseline	1 Month	3 Months	6 Months	9 Months
Pro-brain natriuretic peptide	ProBNP	x		x		x
Microalbumin, urine	UMA	x		x		x
high sensitivity C-reactive protein	hsCRP	x		x		x
Lipid panel	BLIP	x		x		x
Fasting glucose	Glu	x		x		x
Urine pregnancy test (if appropriate)	HCGU	x				

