12.1 Statistical Methodology

The primary analysis of the study is descriptive, to obtain a point estimate and 95% confidence interval of the difference in small artery elasticity (C_2) between nebivolol and atenolol treatment arms and nebivolol and placebo at the end of the observation period (9 months). Point estimates and 95% confidence intervals for the improvement in C_2 within each treatment will also be presented.

Secondary analysis estimating difference in Rasmussen Disease Score (RDS) improvement between the nebivolol and atenolol treatment groups along with nebivolol and placebo groups at the end of the observation period (9 months) will also be completed.

Other secondary analyses include estimates of the associations among changes in RDS as well as risk factor and biomarker measurements from baseline to the 3, and 9 month time points in the two positive comparator groups.

Unpaired t-tests will be used to compare the means of C_2 (small artery elasticity) as well as all RDS test component and biomarker values for each subject group at each time point. Paired t-tests will be used to compare baseline values and values from subsequent time points within one group. A P-value of < 0.05 will be considered statistically significant.

Comparison of sensitivity and variability for C₂ and flow-mediated dilation (FMD) methodologies used in quantifying endothelial function of each group over the 9 month study period will also be included in the secondary analyses. Data will be analyzed within and between test groups with a significance level of $P \leq 0.05$.

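### The C2 reading that qualifies a patient is also the baseline for change, so within-arm C2 improvement is biased upward by regression to the mean

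*Combined protocol and SAP*

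**What the plan says.** - **Selection on C2.** Section 5.1 requires "Borderline or abnormal small artery elasticity". Section 6 places randomization "after eligibility is confirmed by measuring blood pressure and small artery elasticity".
- **When C2 is measured.** In the Schedule of Events (8.1), the row beginning "Arterial elasticity (small and large" is marked at Screen and at 1, 3 and 9 months; the Baseline cell is empty. Flow-mediated dilation (FMD) is marked at Baseline and not at Screen. The Study Schema lists C2 "and flow-mediated dilation at 0, 1, 3 and 9 months", which is a single pre-treatment time point.
- **What is done with it.** Section 9.1 defines the primary endpoint as the change in C2 from baseline to 9 months. Section 12.1 makes the between-arm difference at 9 months the primary analysis. It adds that point estimates and "95% confidence intervals for the improvement in C_2 within each treatment will also be presented". It also says "Paired t-tests will be used to compare baseline values and values from subsequent time points within one group", with significance at P < 0.05.
- **C2 against FMD.** Objective 4.2.4 and endpoint 9.2.4 compare the two methods' sensitivity to change. For this comparison 12.1 says "Data will be analyzed within and between test groups".
- **Hypothesis.** Section 1 expects that "only nebivolol will improve impaired endothelial function".

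**The concern.** A group selected for low readings on an imperfectly repeatable measure will, on average, read higher the next time. Higher C2 counts as improvement, so selection alone moves every arm in the favourable direction when the selecting reading is the reference. Section 12.1 attaches confidence intervals and P-values to that movement and does not say how they should be read.

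Two conclusions are exposed. First, the hypothesis that only one drug improves endothelial function invites an arm-by-arm reading. A paired test can show improvement on atenolol or placebo where there is none, or overstate it on nebivolol. Second, FMD is not an entry criterion and has its own Baseline reading, so it carries no such shift. In a within-group comparison C2 can therefore look more responsive than FMD when neither has changed.

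The primary nebivolol-atenolol and nebivolol-placebo estimates are not at stake. All arms are selected in the same way before randomization, so the shift cancels.

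**Working it through.** **Is the qualifying reading the reference?** In 8.1 only resting blood pressure and arterial elasticity are marked at Screen, and these are the two eligibility measurements named in section 6. FMD, carotid thickness, ECG and left ventricular ultrasound show the reverse pattern. The row therefore looks deliberate. Month 0 in the Schema adds no second reading, and no section schedules one or defines the C2 baseline otherwise.

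**The plan's own figure.** Section 12.2 gives a difference of 3.3, SD 3.57, α = 0.05 and power 0.9. Two-sided, n = 2 × [3.57 × (1.960 + 1.282) / 3.3]² = 24.6, so 25 per arm. The stated size reproduces, and n = 25 is used below.

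**Null model.** The documents do not give the retest correlation ρ, the eligible fraction q or the cut-off, so these are assumed: normal C2, the lowest fraction q eligible under a single cut-off, ρ from 0.6 to 0.9, and no treatment effect. With c the q-quantile and φ the normal density:

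expected within-arm shift = (1 − ρ) × φ(c) / q, in SDs of unselected C2.

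The rejection rates come from simulation (n = 25 per arm, 40,000 runs per cell). They count two-sided 0.05 paired t-tests that reject in the direction of improvement, for which the nominal rate is 2.5%. They do not depend on the SD.

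| Eligible q | φ(c)/q | Shift in SD, ρ = 0.9 / 0.6 | Units at SD 3.57 | Improvement declared |
|---|---|---|---|---|
| 25% | 1.271 | 0.127 / 0.508 | 0.45 / 1.82 | 28.6% / 84.3% |
| 50% | 0.798 | 0.080 / 0.319 | 0.28 / 1.14 | 14.1% / 44.7% |
| 75% | 0.424 | 0.042 / 0.169 | 0.15 / 0.61 | 6.6% / 15.6% |
| 90% | 0.195 | 0.020 / 0.078 | 0.07 / 0.28 | 4.0% / 6.2% |

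**Hand check of one cell (q = 50%, ρ = 0.6).** The variance of screening values after selection is 1 − 0.798² = 0.363. The variance of change is 0.4² × 0.363 + (1 − 0.6²) = 0.698, so the SD is 0.836 and the standard error 0.836/5 = 0.167. The shift is 0.319/0.167 = 1.91 standard errors. Against a critical value of 2.064 this gives a rejection rate of about 44%, in line with the simulated 44.7%.

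**Lenient case from the plan's own SDs.** Suppose 3.57 is the SD of unselected C2 levels and 3.0 is the SD of screening values after selection. The ratio 3.0/3.57 = 0.84 then corresponds to q = 0.896. The shift is 0.07 (ρ = 0.9) to 0.29 units (ρ = 0.6), and improvement is declared in 4.1% to 6.5% of arms.

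**C2 against FMD within one arm.** FMD is simulated as an unselected null change, independent of C2, and the two are compared on mean change divided by SD of change. C2 shows the larger value in 63% to 98% of runs for q = 25% to 75%, instead of 50%. Hand check at the mild end (q = 75%, ρ = 0.9): the variance of screening values is 0.535, so the SD of change is √(0.1² × 0.535 + 0.19) = 0.442. The standardized shift is 0.042/0.442 = 0.096, and Φ(0.096 × 5/√2) = Φ(0.34), or about 63%.

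**Between arms.** Unpaired t-tests on the same simulated data reject in 4.8% to 5.3% of runs, both for 9-month values and for changes.

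**The case against.** The strongest reply is that little depends on the within-arm results. The primary analysis is a randomized contrast, the trial is described as a preliminary Phase II estimate, within-arm figures are an addition, and the placebo arm shows any shift openly. That is true and limits the severity. However, a paired test within the nebivolol or atenolol arm makes no use of the placebo arm, and nothing in 12.1 tells the reader to.

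Second, no section expressly defines the C2 baseline, and month 0 in the Schema could mean the Baseline visit. If C2 is in practice repeated there and that value is used, the bias goes. But the plan as written schedules one pre-treatment reading.

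Third, the size is assumed. The one case tied to plan figures is mild: 0.07 to 0.29 units is 2% to 9% of the 3.3-unit target. If 3.0 is the screening SD after selection, then 25%, 50% and 75% eligible would imply SDs of 1.75, 2.15 and 2.61, all below it. This stands as a caution against the upper end of the range. It does not exclude larger shifts, because 12.2 does not say whether its SDs describe levels or changes, or at which visit.

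Fourth, section 3 allows categories stratified by age and gender, whereas one cut-off was modelled. FMD was taken as independent of C2, on a metric that the plan does not define. These points affect the size and not the direction.

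**Conclusion.** The concern holds. If the plan is followed as written, within-arm C2 improvement, its confidence intervals and its paired t-tests are biased upward in expectation, and the within-group part of the C2-versus-FMD comparison is tilted towards C2. The direction needs only selection on low C2 and a retest correlation below 1.

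The size is illustrative. At SD 3.57 the shift is 0.15 to 1.82 units for 25% to 75% eligible and ρ of 0.6 to 0.9, with false declarations of improvement in about 7% to 84% of arms against a nominal 2.5%. In the lenient case the rate is about 4% to 6%, so the practical effect may be small. The primary between-arm estimates and the sample size are unaffected. The plan should be changed because it specifies tests at P < 0.05 whose error rate is not the nominal one, and the correction costs almost nothing. Nothing is claimed here about blood pressure.

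**What to change.** **In 12.1:**

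1. Name the reading that serves as the C2 baseline, and reconcile the Schema with 8.1.
2. Do not use within-arm paired t-tests of C2 to claim improvement. Present within-arm C2 change descriptively, with a note that it includes regression to the mean because the screening value is the reference.
3. Base any claim of improvement on the contrast with placebo or atenolol.
4. Base the C2-versus-FMD comparison on between-arm differences. One option is the nebivolol minus placebo difference divided by its SD for each method, with a bootstrap confidence interval for the difference between methods.

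The cost is wording and the loss of within-arm P-values for C2.

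**Optional:** repeat C2 at the already scheduled Baseline visit, use that value alone as the analysis baseline, and keep the screening value for eligibility only. This is one extra non-invasive reading per patient, about 75 in all, on equipment already in use. In simulation it returns the rate of false improvement to 2.3% to 2.6%, provided the retest correlation does not depend on the time between readings. Averaging the two readings is not enough, since it only halves the bias (1.14 to 0.57 units at q = 50%, ρ = 0.6).

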12.2 Design and Sample Size Justifications

A sample size of 25 subjects per arm will be adequate to detect a difference in small artery elasticity of 3.3 units (ml/mm Hg x 100) between positive comparators when power = 0.9 and $\alpha = 0.05$. This is assuming a standard deviation of ± 3.57 units. This assumption is made based on a previous clinical trial measuring small artery elasticity in patients undergoing anti-hypertensive therapy [14].

Subjects in the previous study were not selected on the basis of C₂ as they are in EVIDENCE. Therefore, it is reasonable to assume that our actual standard deviation will be much smaller than our estimate giving us a conservative population sample of 75. Assuming a smaller deviation of 3.0 (instead of 3.57) we would still have an adequate sample with a dropout rate of 7.6%. If rates of attrition exceed 7.6%, subjects will be replaced

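### Section 12.1 calls the primary C2 analysis descriptive, yet its blanket P < 0.05 rule lets any between-arm or within-arm t-test, primary or secondary, be declared statistically significant

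*Combined protocol and SAP*

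**What the plan says.** Section 12 describes a Phase II trial meant to give a preliminary estimate of effect. Section 12.1 opens in that spirit: "The primary analysis of the study is descriptive, to obtain a point estimate and 95% confidence interval" for the C2 difference at 9 months, nebivolol against atenolol and nebivolol against placebo. Total RDS is also framed as estimation ("Secondary analysis estimating difference in Rasmussen Disease Score (RDS) improvement").

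The testing paragraph of 12.1 is different in kind. It applies unpaired t-tests to C2 "as well as all RDS test component and biomarker values for each subject group at each time point". It continues: "Paired t-tests will be used to compare baseline values and values from subsequent time points within one group". It ends: "A P-value of < 0.05 will be considered statistically significant". The paragraph on C2 and FMD has its own threshold: "Data will be analyzed within and between test groups with a significance level of" P ≤ 0.05.

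Section 12.2 attaches alpha 0.05 and a power figure to one comparison. Twenty-five per arm is said to be enough to "detect a difference in small artery elasticity of 3.3 units (ml/mm Hg x 100) between positive comparators when power = 0.9". Section 12.1 speaks of two positive comparator groups, so this is read as nebivolol against atenolol.

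Sections 9.1 and 9.2 separate one primary endpoint (9-month change in C2) from the secondary endpoints. No section says which results the significance rule is for, or calls any P-value nominal or exploratory.

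**The concern.** A descriptive primary analysis and an unrestricted declaration of significance do not fit together. If the aim is estimation, there is no reason for the declaration to reach every component, biomarker and visit. If some result is meant to carry a formal claim, the plan should name it.

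Two consequences matter for the trial report. First, with this many tests at 0.05, a few significant secondary findings are expected by chance, and the plan permits them to be reported as such. Second, the paired tests invite a comparison they cannot support. Section 1 hypothesizes that only nebivolol will improve endothelial function. A significant change from baseline in the nebivolol arm beside a non-significant one in the atenolol arm would look like confirmation, although no test between the arms has been made.

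**Working it through.** **1. The plan's own figure.** Inputs from 12.2: difference 3.3, SD 3.57, power 0.9, alpha 0.05 (sidedness not stated).

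- Normal approximation, two-sided: n = 2 × [3.57 × (1.960 + 1.282) / 3.3]² = 24.59, rounded up to 25 per arm. This reproduces the plan; one-sided alpha would give 21.
- Power at 25 per arm: 0.905 by the normal approximation, 0.893 by the t-test.

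The sample size is therefore in order for the comparison it names.

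**2. Between-group tests under the rule.** Measures come from 9.1, 9.2.2 and 9.2.3, visits from the schedule in 8.1. The two comparisons are those named for C2 and RDS in 12.1.

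| Measure | Post-baseline visits | Measure-by-visit cells |
|---|---|---|
| C2 | 1, 3, 9 months | 3 |
| Large artery elasticity | 1, 3, 9 months | 3 |
| Resting blood pressure | 1, 3, 6, 9 months | 4 |
| Seven other RDS components | 3, 9 months | 7 × 2 = 14 |
| Total cholesterol, LDL, HDL, triglycerides, hsCRP, glucose | 3, 9 months | 6 × 2 = 12 |
| Total | | 36 |

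- Every scheduled visit: 36 × 2 comparisons = 72 tests; 72 × 0.05 = 3.6 expected false positives if every null is true.
- Months 3 and 9 only: 16 measures × 2 visits × 2 comparisons = 64 tests; 64 × 0.05 = 3.2.
- Removing the two 9-month C2 contrasts leaves 72 − 2 = 70, or 64 − 2 = 62.

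The expected counts hold whatever the correlation between outcomes. The chance of at least one false positive does depend on that correlation, which the documents do not give, so no figure is offered for it.

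**3. Within-arm tests.** 36 × 3 arms = 108, or 32 × 3 = 96 at months 3 and 9 only.

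**4. FMD, if analysed by simple t-tests.** At 1, 3 and 9 months: 3 × 2 between arms + 3 × 3 within arms = 15. At 3 and 9 months: 4 + 6 = 10. These are not in the counts above.

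**5. Significant in one arm but not in the other.** Assume that nebivolol and atenolol improve equally and that each paired test has power p. The arms are independent, so the chance of a significant nebivolol change with a non-significant atenolol change is p(1 − p). The documents give no p. For p = 0.3, 0.5 and 0.8 it is 0.21, 0.25 and 0.16.

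**6. The two 9-month C2 contrasts.** They share the nebivolol arm, so with equal arms their correlation is 0.5. If all three arms are equal, the chance that at least one statistic exceeds 1.96 in absolute value is 0.091 (bivariate normal), and 0.045 if only results favouring nebivolol count. Nebivolol against atenolol alone keeps its 0.05.

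**The case against.** This is a preliminary Phase II trial, and unadjusted secondary analyses are normal in one. Section 9.1 fixes one primary endpoint at one time point. Section 9.2 and the wording of 12.1 label the rest as secondary, so a biomarker P-value does not arrive with the standing of the primary result. All of this stands, and no multiplicity adjustment is asked for. It does not answer the point, because the sentence declaring significance makes no distinction between primary and secondary.

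The counts also depend on reading. Section 12.1 does not say which pairs of arms the t-tests compare. All three pairs would give 36 × 3 = 108 between-group tests, and baseline tests would add more. Electrocardiogram and retinal findings may not suit a t-test; dropping both removes 2 × 2 × 2 = 8 tests. The counts are therefore illustrative, though the conclusion is the same on any of these readings.

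Some stronger readings are tempting, and the documents do not support them:

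- **That the 9.1% breaks a promise.** The plan nowhere undertakes to hold 5% across both C2 contrasts, and it states no rule that either one suffices for success. The contrasts answer different questions.
- **That it is unclear whether 9-month C2 is tested.** C2 is named in the t-test sentence, so it is both estimated and tested. The tension lies in the word descriptive.
- **That the placebo comparison is underpowered.** With 1:1:1 allocation, 25 per arm and the same SD, it has the same 0.893 power for a 3.3-unit difference. Section 12.2 simply does not state it.
- **That placebo should be demoted.** Sections 4.1, 12 and 12.1 put atenolol and placebo together in the primary objective and analysis. Removing one would change the design intent.

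**Conclusion.** The point holds as a defect in the significance rule. It is not an error in the sample size or in the choice of primary endpoint. Followed as written, 12.1 allows about 64 to 72 between-group results, all but two of them outside 9-month C2, and 96 to 108 within-arm results to be declared significant at 0.05.

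The 3.2 to 3.6 expected false positives assume that every null is true. The number will be lower if some effects are real, as Section 1 expects for blood pressure under both drugs and for endothelial function under nebivolol. The counts assume two nebivolol comparisons and the visits in 8.1.

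This is not fatal: the comparison sized in 12.2 keeps its 5% error rate. The correction is worth making before analysis because it is cheap and governs what the report may claim.

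**What to change.** In 12.1, replace both blanket rules (< 0.05 and ≤ 0.05) with text such as:

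> The primary results are the 9-month C2 differences, nebivolol versus atenolol (the comparison powered in 12.2) and nebivolol versus placebo, each with its 95% CI. All other visits, RDS and its components, biomarkers, FMD and within-arm changes are reported as estimates with 95% CIs. Their P-values are nominal, unadjusted for multiplicity, and support no claim of statistical significance. Within-arm tests will not be used to infer a difference between treatments.

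This keeps the descriptive aim and both primary comparisons. If the sponsor wants a formal test of C2, limit it to nebivolol versus atenolol at two-sided 0.05, optionally followed by nebivolol versus placebo at 0.05 only if the first is significant, and reword the descriptive label to match.

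**Cost.** Fewer secondary results can be called significant. Sample size does not change, nor does the power of the sized comparison (about 0.89 at 25 per arm, difference 3.3, SD 3.57). That power assumes the SD applies to the quantity tested; 12.2 does not say whether 3.57 refers to C2 values or to changes.

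With the optional second step, the power to win both is about 0.82 by simulation if the true placebo difference is also 3.3. The documents give no placebo difference. Assumed values of 2.5 and 4.0 give about 0.64 and 0.88 in the same simulation.

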4.2. Secondary Objectives

- 4.2.1 Evaluate the effects of nebivolol as compared to atenolol and placebo on cardiovascular health in subjects with early vascular disease as measured by change in Rasmussen Disease Score (RDS) over a 9 month study period.
- 4.2.2 Evaluate changes in each RDS component over the 9 month study period in all treatment groups.
- 4.2.3 Evaluate the changes in risk factor and biomarker measurements from baseline to 3 and 9 month time points in all treatment groups.
- 4.2.4 Compare the sensitivity of pulse contour analysis and flow-mediated dilation methodologies for measuring functional changes in the endothelium and quantifying endothelial dysfunction.

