9.2 Secondary Endpoints

9.2.1 Change in Rasmussen Disease Score (RDS) from baseline to 9 months after intervention initiation. Each test is scored as 0 for normal, 1 for borderline, and 2 for abnormal. The criteria for normal, borderline, and abnormal has been established on the basis of large public databases. The ten cardiovascular tests provide total scores ranging from 0 (low risk) to 20 (high risk).

9.2.2 Change in each of the CDS components as measured from baseline to 3 and 9 months.

- Blood pressure at rest
- Large artery elasticity
- Treadmill exercise test
- Carotid intima-medial thickness
- Electrocardiogram (ECG)
- Left ventricle ultrasound
- Retinal vasculature
- Microalbuminuria
- NT-proBNP

9.2.3 Change in risk factor and biomarker measurements as measured from baseline to 3 and 9 months.

- Total cholesterol, LDL, HDL, and triglycerides
- hsCRP
- blood glucose

9.2.4 Difference in endothelial function quantification and sensitivity to change between pulse contour analysis and flow-mediated dilation from baseline to 9 months after intervention initiation.

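### The tests stated for the C2 versus FMD comparison never contrast the two methods, so they do not answer the question in objective 4.2.4 of which is more sensitive to change

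*Combined protocol and SAP*

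**What the plan says.** Section 4.2 sets the aim: "Compare the sensitivity of pulse contour analysis and flow-mediated dilation methodologies for measuring functional changes in the endothelium and quantifying endothelial dysfunction". Section 9.2 turns it into an endpoint: "Difference in endothelial function quantification and sensitivity to change between pulse contour analysis and flow-mediated dilation from baseline to 9 months after intervention initiation". Neither section defines sensitivity or names a statistic.

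The last paragraph of Section 12.1 says that a comparison of the sensitivity and variability of the two "methodologies used in quantifying endothelial function of each group over the 9 month study period will also be included in the secondary analyses". It then adds "Data will be analyzed within and between test groups with a significance level of" P ≤ 0.05.

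The tests named earlier in Section 12.1 are of two kinds:

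- Unpaired t-tests compare subject groups on C2 "as well as all RDS test component and biomarker values for each subject group at each time point". FMD is not named in this list, and Section 9.2.2 does not count it among the score components.
- For change over time, "Paired t-tests will be used to compare baseline values and values from subsequent time points within one group".

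The study schema has both methods measured in the same patients at 0, 1, 3 and 9 months. Section 5.1 requires borderline or abnormal C2 for entry and sets no FMD criterion. In the Section 8.1 schedule, arterial elasticity is marked at Screen and not at Baseline, while FMD is marked at Baseline.

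**The concern.** The question is about a difference between two methods. The stated tests concern differences between arms, or between visits, for one method at a time. C2 is expressed in ml/mm Hg × 100 and FMD is derived from brachial artery diameter, so their raw differences cannot be set against each other. No common scale is defined. The only criterion in the text that applies to both is whether P reaches 0.05, and a significant result for one method beside a non-significant result for the other is not evidence that the methods differ.

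There is also an asymmetry. C2 decides who enters and FMD does not. A value chosen for being low tends to rise on repeat measurement without any treatment, so within-group change flatters C2. Section 3 already expects FMD to be the less sensitive method, and this artefact would look like confirmation.

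At stake is a numbered secondary objective that Section 3 gives as a reason for measuring both. The descriptive primary analysis of C2 is not affected.

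**Working it through.** **Inputs from the documents (Section 12.2).** 25 per arm, C2 difference 3.3, SD 3.57, power 0.90, α = 0.05. The documents give no FMD effect, no FMD SD and no C2-FMD correlation, so these are assumed and varied.

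**The plan's own figure.** n = 2(1.960 + 1.282)² × 3.57² / 3.3² = 2 × 10.51 × 12.74 / 10.89 = 24.6, which rounds up to 25 per arm. The stated size reproduces (power 0.905 by the normal formula, 0.893 by the t-test). The planning effect is 3.3 / 3.57 = 0.92 SD. No figure is stated for the method comparison.

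**Discordant verdicts when the methods are equally sensitive.** Suppose both have the same true standardised effect d and each is tested between two arms of 25. With uncorrelated measurements and power p, exactly one is significant with probability 2p(1 − p):

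- d = 0.92: p = 0.893, so 2 × 0.893 × 0.107 = 0.191.
- d = 0.60: p = 0.547, so 2 × 0.547 × 0.453 = 0.496.

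Correlation lowers these values. Simulation (40,000 trials per setting, correlation 0 to 0.5) gives:

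| True effect, both methods | Exactly one method significant |
|---|---|
| 0.92 SD | about 14-20% |
| 0.75 SD | about 27-39% |
| 0.60 SD | about 33-50% |

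**The reverse error.** With true effects of 1.2 and 0.9 SD and correlation 0 to 0.6, the two verdicts agree in 87-88% of trials, so a real difference would usually go unseen.

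**Selection on C2.** As an illustration, take no treatment effect, 25 patients drawn from the lower half of the C2 distribution, and an assumed test-retest correlation r. The mean of the lower half of a normal distribution lies 0.80 SD below the centre, so the expected rise is (1 − r) × 0.80 SD: 0.24 SD at r = 0.7 and 0.08 SD at r = 0.9. The paired test on C2 is then significant in about 34% and 14% of trials instead of 5%. FMD, which is not used for selection, is not inflated to the same degree.

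**Precision of a direct contrast.** For the difference between two standardised effects with common d and correlation ρ, the variance is approximately 2[(2/n)(1 − ρ) + (d²/4n)(1 − ρ²)]. At d = 0.92, ρ = 0, n = 25 this is 2(0.080 + 0.0085) = 0.177, giving a 95% half-width of 1.96 × 0.421 = 0.82 SD (0.85 by simulation). Over d = 0.3 to 0.92 and ρ = 0 to 0.6, the simulated half-width runs from 0.51 to 0.85 SD.

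**The case against.** The strongest reply is that Section 12.1 does not say the methods will be ranked by their P values. It promises a comparison of sensitivity and variability, and unit-free summaries such as a coefficient of variation or change divided by its SD would fit that sentence. A reader might infer that the plan will call a method more sensitive because it alone reaches P ≤ 0.05. The documents do not support this: no such decision rule appears anywhere. The percentages above are therefore rates of discordant P values, not rates at which the trial reaches a wrong conclusion. They rest on an assumed FMD effect and correlation, and the 0.92 SD setting, the only one tied to the documents, is documented for C2 alone and gives the lowest range in the table. This part of the objection stands.

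A reader might also infer that the trial cannot answer the objective at all. That does not follow either, since both methods are measured in the same patients.

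Two further points stand. The objective also covers quantification of dysfunction, and Section 12.1 adds variability; a single treatment-response contrast does not cover these. And a direct contrast will be imprecise: power to separate 0.92 from 0.60 SD is only about 12-18%.

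None of this supplies the missing step. A stated intent to compare, followed only by tests that make no such comparison, leaves the objective without an analysis.

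On selection, the schema lists C2 at month 0, which could suggest a separate baseline reading. The Section 8.1 schedule marks only the screening measurement before treatment.

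**Conclusion.** The point holds in a limited form. The tests and the criterion in Section 12.1 contain no contrast between C2 and FMD, no other section supplies one, and carrying out the stated tests would not answer objective 4.2.4. Separate verdicts at P ≤ 0.05 can neither establish nor exclude a difference in sensitivity. The 14-20% (0.92 SD) and 33-50% (0.6 SD) illustrate what would happen if those verdicts were used as the comparison, assuming 25 per arm, equal effects and correlation 0 to 0.5.

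The tilt of within-group change towards C2 follows from the entry criterion and the visit schedule. Its size depends on repeatability and on how strict the selection is, and the documents give neither.

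This is a secondary objective in a Phase II study aimed at a preliminary estimate. The change is worth making, but nothing in the primary analysis or the sample size depends on it.

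**What to change.** Add a short paragraph to Section 12.1, before unblinding:

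1. For each method, estimate the between-arm difference at 9 months (nebivolol minus atenolol, and nebivolol minus placebo), adjusted for that method's own baseline, and divide it by the residual SD of that model.
2. For each contrast, report the C2 standardised effect minus the FMD standardised effect, with a 95% confidence interval from a bootstrap that resamples patients and keeps both measurements of a patient together.
3. Label the comparison exploratory and state the expected half-width, roughly 0.5-0.85 SD, so that a wide interval is not read as equivalence.
4. Do not base the sensitivity conclusion on within-group change from the screening C2. Between-arm effects avoid the problem because randomisation spreads the selection artefact evenly over the arms.
5. Describe the variability of each method separately, for example from the placebo arm.

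The cost is one paragraph and one bootstrap on data already being collected. No visits, measurements or patients are added. The gain is an honest interval; at this sample size it will often not settle which method is more sensitive.
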